3.4.2 Statistical Methodology of Efficacy Analyses

Tumor Response Data

The following tumor response variables will be listed and summarized using descriptive statistics:

- Best Overall Response,
- DCR per RECIST 1.1,
- DCR as per iRECIST (iDCR),
- Progression Free Survival per RECIST (PFS),
- Progression Free Survival per iRECIST (iPFS), and
- Overall Survival (OS).

The Disease Control Rate will be based on the number of patients achieving a PR, CR, or stable disease ≥16 weeks based on RECIST v1.1 and iRECIST (iDCR).

Point estimates along with the exact Clopper-Pearson 95% CIs will be presented for DCR and iDCR.

The best overall response will be determined according to RECIST v1.1 and iRECIST. Response (CR/PR, iCR/iPR) must be confirmed by a repeat assessment performed no less than 6 weeks (42 days) after the criteria for response are first met. When SD or iSD is believed to be the best response, it must also meet the minimum interval of 6 weeks (42 days) from the start of study drug. If the minimum time is not met when SD or iSD is otherwise the best time point response, the patient's best response depends on the subsequent assessments.

All tumor response data will be listed by patient and tabulated by study arm.

Progression Free Survival

PFS and iPFS based on the Investigator assessment will be estimated using the Kaplan-Meier method.

The Kaplan-Meier estimate of the first quartile, median, and third quartile for PFS and iPFS and the 95% CIs for the median calculated using the Brookmeyer-Crowley method will be presented. The PFS and iPFS rates and 95% CIs will also be provided for 6 and 12months after the first treatment with CyPep-1 + pembrolizumab using the Kaplan-Meier method.

Overall Survival

OS based on the Investigator assessment will be estimated using the Kaplan-Meier method.

The Kaplan-Meier estimate of the first quartile, median, and third quartile for OS and the 95% CIs for the median calculated using the Brookmeyer-Crowley method will be presented.

3.5 Pharmacokinetic (PK) Assessment

Pharmacokinetic (PK) analyses will be described in a separate document.

3.6 Biomarker Assessment

All available biomarker data will be listed by patient.

3.7 Safety Assessment

Safety will be assessed by physical examinations, vital signs, 12-lead ECGs, ECOG performance status (see Protocol Appendix C), clinical laboratory evaluations, and AEs (as defined by the National Cancer Institute [NCI] CTCAE v5.0; see Section 8.1.3 of the protocol) as indicated in the Schedule of Assessments (Protocol Appendix A). Additional assessments may be performed as clinically indicated.

Patients will be monitored for DLTs for confirmation of the CyPep-1 dose of 20 mg Q2W in combination with pembrolizumab 400 mg Q6W. Safety will be monitored in conjunction with the DMC and as per the DMC charter.

Safety data will be summarized in total based on the safety analysis set.

3.7.1 Adverse Events (AEs)

AEs will be captured from the date of informed consent through study completion. All AEs will be coded to system organ class and preferred term using MedDRA version 25.0. Treatment-emergent adverse events (TEAEs) are defined as AEs that start or worsen after the first dose of study drug and within 30 days after the last dose of study treatment.

Adverse events of clinical interest (AECI) include the following:

- An overdose of pembrolizumab, as defined in Section 5.5.3.4 of the protocol; and
- An elevated aspartate aminotransferase (AST) or alanine aminotransferase (ALT) laboratory value that is greater than or equal to 3 times the upper limit of normal (ULN) (greater than 5 times the ULN for patients with liver metastases), an elevated total bilirubin laboratory value that is greater than or equal to twice the ULN, and, at the same time, an alkaline phosphatase laboratory value that is less than twice the ULN, as determined by way of protocol-specified laboratory testing or unscheduled laboratory testing.

An overview of TEAEs will be provided including counts and percentages of patients (and event counts) with the following:

- TEAEs;
- CyPep-1 related TEAEs (overall and by maximum severity);
- TEAEs related to any Investigational Medicinal Product (IMP) (CyPep-1 or pembrolizumab);
- CTCAE Grade 3/4/5 TEAEs;
- Treatment-emergent serious AEs (TESAEs);
- CyPep-1 related TESAEs;
- TESAEs related to any IMP (CyPep-1 or pembrolizumab);
- Serious adverse events (SAEs);
- TEAEs leading to interruption of CyPep-1;
- TEAEs leading to interruption of pembrolizumab;
- TEAEs leading to delayed or held CyPep-1 dose;
- TEAEs leading to delayed or held pembrolizumab;
- TEAEs leading to permanent discontinuation of CyPep-1;
- TEAEs leading to discontinuation of pembrolizumab;
- TEAEs leading to discontinuation of study;
- · TEAEs leading to death; and
- TEAEs of clinical interest.

Counts and percentages of patients (and event counts) will also be presented by system organ class (SOC) and preferred term (PT) for each of the categories in the overview. For these summaries, patients with multiple adverse events will be counted only once per SOC or PT.

A by-patient adverse event data listing will be presented including, but not limited to, verbatim term, preferred term, SOC, CTCAE grade, and relationship to any study drug. SAEs, and AEs leading to discontinuation of study drug, AEs leading to death, and AECIs will also be listed.

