8.1 Adverse Events

An AE is defined as any untoward medical occurrence in a clinical investigation patient administered a pharmaceutical product, which does not necessarily have a causal relationship with this treatment. An AE can therefore be any unfavorable and/or unintended sign (including an abnormal laboratory finding), symptom, or disease temporally associated with the use of an investigational medicinal product, whether or not related to the investigational medicinal product. All AEs, including observed or volunteered problems, complaints, or symptoms, are to be recorded on the appropriate eCRF.

AEs, which include clinical laboratory test variables, will be monitored and documented from the time of signing the ICF until 30 days after the last dose of study treatment. All AEs that are considered serious, from the time of signing the ICF until 90 days (30 days if patients initiate new anti-cancer therapy) after the last dose of study treatment, will also be monitored and documented. Patients should be instructed to report any AE that they experience to the Investigator, whether or not they think the event is due to study treatment/procedure. Beginning at screening, Investigators should make an assessment for AEs at each visit and record the event on the appropriate AE eCRF.

Wherever possible, a specific disease or syndrome rather than individual associated signs and symptoms should be identified by the Investigator and recorded on the eCRF. However, if an observed or reported sign or symptom is not considered a component of a specific disease or syndrome by the Investigator, it should be recorded as a separate AE on the eCRF. Additionally, the condition that led to a medical or surgical procedure (eg, surgery, endoscopy, tooth extraction, or transfusion) should be recorded as an AE, not the procedure itself.

Any medical condition already present prior to signing of the ICF should be recorded as medical history and not be reported as an AE unless the medical condition or signs or symptoms present at baseline changes in severity, frequency, or seriousness at any time during the study. In this case, it should be reported as an AE.

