10.3 End of Study

The end of the study ("study completion") is defined as the date of the last protocol-specified visit/assessment for the last patient in the study.

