3.1.6 Handling of Dropouts and Missing Data

In general, missing data values will be recorded as missing and will not be imputed for the statistical analysis unless specified otherwise.

For missing or partial AEs and concomitant medications (CM) dates, conservative conventions will be applied in order to assign the events to corresponding periods (e.g. treatment period to ensure that no TEAE is missed). AEs will be considered as treatment-emergent, and the medications will be considered as concomitant if the missing/partial dates cannot definitively exclude the treatment period. Handling incomplete dates (e.g., AE and concomitant medications) are described in Appendix E.

Treatment duration

For the calculation of treatment duration, the date of last study drug infusion should be consistent with that of the last dose on the dosing page of the electronic case report form (eCRF). If the date of last dose on the dosing page is missing on the eCRF, use the last available dose date on the dosing page of eCRF to calculate. The last infusion should be clearly recorded on eCRF and not be estimated by the date of returning remaining study drug.

Laboratory values

Unless otherwise specified, for laboratory values that are reported using a non-numeric qualifier (e.g., less than [<] or greater than [>] sign), the reported numeric values will be used for summary or analysis without the qualifier.

In some cases, when the White Blood Cells (WBC) count is too low, the WBC differentials may be difficult to detect and thus not reported by the lab. If the reported WBC count < 0.5*10^9/L, then the differentials such as absolute neutrophils value will be imputed as zero for both the lab value summary and the Common Terminology Criteria for Adverse Events (CTCAE) v5.0 grading. For example, absolute neutrophils value imputed as 0 would be considered as grade 4.

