APPENDIX E: DATE OF IMPUTATION GUIDELINE

The following date imputation guidelines will apply to adverse events, prior medications and concomitant medications.

AE Start Date	AE Stop Date	Action
Known	Known/Partial/Missing	If start date < study drug start date, then not TEAE If start date ≥ study drug start date, then TEAE
Partial, but the known date components show that it cannot be on or after study drug start date	Known/Partial/Missing	Not TEAE
Partial, could be	Known	If stop date < study drug start date, then not TEAE
on or after study drug start date		If stop date ≥ study drug start date, then TEAE
	Partial	Impute stop date as latest possible date (ie, last day of month if day is unknown or 31-Dec if day and month are unknown), then:
		If stop date < study drug start date, then not TEAE
		If stop date ≥ study drug start date, then TEAE
	Missing	Assumed TEAE
Missing	Known	If stop date < study drug start date, then not TEAE
		If stop date ≥ study drug start date, then TEAE
	Partial	Impute stop date as latest possible date (ie, last day of month if day is unknown or 31st December if day and month are unknown), then:
		If stop date < study drug start date, then not TEAE
		If stop date ≥ study drug start date, then TEAE
	Missing	Assumed TEAE

CM Start Date	CM Stop Date	Action
Known	Known	If stop date < study drug start date, assign as PRIOR
		If stop date ≥ study drug start date, and start date ≤ end of treatment +30 days, assign as CONCOMITANT
		If stop date ≥ study drug start date and start date > 30 days after the end of treatment, assign as POSTTREATMENT
	Partial	Impute stop date as latest possible date (ie, last day of month if day unknown or 31-Dec if day and month are unknown), then:
		If stop date < study drug start date, assign as PRIOR
		If stop date ≥ study drug start date, and start date ≤ end of treatment +30 days, assign as CONCOMITANT
		If stop date ≥ study drug start date, and start date > 30 days after the end of treatment, assign as POSTTREATMENT
	Missing	If stop date is missing, then PRIOR will never be assumed or assigned
		If start date ≤ end of treatment, assign as CONCOMITANT
		If start date > 30 days after the end of treatment, assign as POSTTREATMENT
Partial	Known	Impute start date as earliest possible date (ie, first day of month if day unknown or 01-Jan if day and month unknown), then:
		If stop date < study drug start date, assign as PRIOR

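### SAP Section 3.7.1 ends the TEAE window 30 days after last dose; the Appendix E adverse event table has no end limit, even for known start dates

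*SAP*

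**What the plan says.** **Definition.** SAP 3.7.1 counts as TEAEs "AEs that start or worsen after the first dose of study drug and within 30 days after the last dose of study treatment". There are two ways in (onset or worsening) and two limits (first dose; last dose plus 30 days).

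**Classification table.** For an adverse event with a known start date, SAP Appendix E says "If start date ≥ study drug start date, then TEAE". A known start before study drug is not a TEAE. The next row, "Partial, but the known date components show that it cannot be on or after study drug start date", is also not TEAE. The remaining rows compare the stop date with study drug start or assume TEAE.

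**Link between the two.** SAP 3.1.6 says "Handling incomplete dates (e.g., AE and concomitant medications) are described in Appendix E". It treats an event as treatment-emergent "if the missing/partial dates cannot definitively exclude the treatment period", and does not define that period.

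**Collection.** Protocol 8.1 collects adverse events "from the time of signing the ICF until 30 days after the last dose of study treatment". It collects serious ones to 90 days, shortened to 30 if new anti-cancer therapy starts. Protocol 8.3 also requires drug-related serious events to be reported outside that period. SAP 3.7.1 describes collection differently: "AEs will be captured from the date of informed consent through study completion".

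**Use.** Incidence, frequency and seriousness of TEAEs is a Phase 1b primary endpoint (SAP 2.2.1).

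**The concern.** The SAP contains two rules for the same flag, and they give different answers for some events. A programmer who follows 3.7.1 and one who follows Appendix E could report different counts of TEAEs and treatment-emergent SAEs (TESAEs) from the same data.

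The events most exposed are serious ones with late onset. They are clinically plausible here: Protocol 5.5.3.3 notes that immune-related events may appear months after the last pembrolizumab dose.

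The missing limit looks like an omission. The medication table in the same appendix cuts at end of treatment plus 30 days in 5 of its 6 rows that have a start date.

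**Working it through.** **Step 1. Read the Appendix E adverse event table row by row.**

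| Row | Start date | Stop date | Test applied | Can return TEAE | 30-day limit |
|---|---|---|---|---|---|
| 1 | Known | Any | Start against first dose | Yes | No |
| 2 | Partial, must precede first dose | Any | None | No | Not applicable |
| 3 | Partial, could be on or after | Known | Stop against first dose | Yes | No |
| 4 | Partial, could be on or after | Partial | Imputed stop against first dose | Yes | No |
| 5 | Partial, could be on or after | Missing | Assumed | Yes | No |
| 6 | Missing | Known | Stop against first dose | Yes | No |
| 7 | Missing | Partial | Imputed stop against first dose | Yes | No |
| 8 | Missing | Missing | Assumed | Yes | No |

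Seven of 8 rows can return TEAE; 0 of those 7 have the limit. Rows 1 and 2 are the only ones in which onset can be known to precede first dose. Neither tests for worsening.

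**Step 2. Classify test events under both rules.** Assumed dates: first dose 10 January, last dose 21 March. Then day 30 after last dose is 20 April and day 90 is 19 June.

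| Event | 3.7.1 | Appendix E |
|---|---|---|
| Known onset 20 April (day 30) | TEAE | TEAE |
| Known onset 21 April (day 31) | Not TEAE | TEAE |
| Known onset 19 June (day 90) | Not TEAE | TEAE |
| Start in May, day unknown, stop missing (days 41 to 71) | Not TEAE | Assumed TEAE |
| Onset 9 January, worsens on treatment, one record | TEAE | Not TEAE |

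For known onsets within the 90-day SAE collection, the rules disagree on days 31 to 90: 90 − 30 = 60 days. If new anti-cancer therapy shortens collection to 30 days, only later drug-related SAEs remain exposed.

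**Step 3. Check the incomplete-date rows against 3.1.6.** The May event cannot fall within 30 days of last dose, whatever the day. The 3.1.6 principle assigns TEAE only if the treatment period cannot be excluded. If that period ends no later than last dose plus 30 days, 3.1.6 would not assign TEAE, yet row 5 does.

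**Step 4. Count the tables that use the flag.** The overview in 3.7.1 lists 17 categories. All but the SAE category use the TEAE or TESAE flag: 17 − 1 = 16. Six of these concern interruption, delay or discontinuation of a study drug, and an event starting more than 30 days after last dose can rarely enter them. That leaves 16 − 6 = 10 that late onset could more readily change.

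**Step 5. Size.** With 6 patients, one patient whose only event in a category is reclassified moves it by 1/6 = 16.7 percentage points; two patients move it by 2/6 = 33.3. A patient already counted in that category moves it by 0.

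**The case against.** **The SAP implies an order.** Section 3.7.1 is worded as a definition, Appendix E is titled as a guideline on date imputation, and 3.1.6 cites it for incomplete dates. Row 1 may be there only to complete the grid, since it accepts any stop date. This stands in part: it makes 3.7.1 the more natural authority. It does not remove the conflict, because row 1 rules on known start dates and row 5 breaks the 3.1.6 principle for incomplete ones. The programming specifications are a separate document, and the text of SAP Section 6 is not visible in the public copy. Either might settle the matter.

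**Collection limits the reach.** This stands. A reader might infer from the SAP's capture sentence that many non-serious late events would be reclassified, because Protocol 10.3 says study completion "is defined as the date of the last protocol-specified visit/assessment for the last patient in the study". The documents do not support that: the protocol sets what sites collect, and Section 8.1 stops non-serious events at day 30. The late-onset effect is therefore essentially on SAEs.

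**Over-inclusion is intended, and incomplete SAE dates should be rare.** Section 3.1.6 does aim to miss no TEAE, SAEs are reported within 24 hours of awareness, and missing data are queried. This weakens the May example. It does not touch known onsets on days 31 to 90.

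**The worsening gap is small.** This stands. It covers only events starting between consent and first dose, and only if worsening stays in the same record; the documents do not show how the eCRF records it. Worsening of a pre-consent condition is already reported as an adverse event under Protocol 8.1.

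**After first dose versus on or after.** This is a minor wording difference, natural when only dates are compared.

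**Conclusion.** The conflict is real and should be corrected, but its reach is limited. Two written rules classify SAEs starting after day 30 differently for a primary endpoint. A smaller difference affects events that start before first dose and worsen on treatment. The number of affected events is unknown. The 16.7-point step assumes that all 6 planned patients are in the Safety Analysis Set.

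Three stronger readings are not supported:

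- That the SAP gives no indication of which rule governs. Section 3.1.6 and the appendix title point to 3.7.1; what is missing, in the visible text, is a statement that it overrides the table.
- That dose confirmation is at risk. It rests on dose-limiting toxicities in Cycle 1, defined in Protocol 3.1.1.1 without the TEAE flag.
- That late SAEs would be lost if 3.7.1 is followed. They stay in the all-SAE category, its system organ class and preferred term table, and the listings.

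The analysis is descriptive, so no test or error rate is involved.

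**What to change.** Amend the SAP before database lock:

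- **(a) Precedence.** State that 3.7.1 defines TEAE and that Appendix E only resolves incomplete dates.
- **(b) Known-start row.** Delete it from the adverse event table, or align it with 3.7.1, including the 30-day limit and worsening. Say how worsening is identified: by a separate record or by a grade-change date. If the eCRF captures neither, say that worsening within one record cannot be identified.
- **(c) Incomplete dates.** Assign TEAE unless the known components exclude the window from first dose to last dose plus 30 days. Define the treatment period in 3.1.6 as that window.
- **(d) First-dose boundary.** Use the same one in both places. On or after is the conservative choice when only dates are available. It changes the present wording of 3.7.1 and should be recorded as a change.

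The cost is a few sentences, some table cells and the matching program edits. The 30-day window stays as it is, and no new data are needed. If the database is already locked, SAP Section 1 provides for the change to be documented in the study report.

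The medication table's row for known start and missing stop leaves days 1 to 30 after treatment unassigned. That is a separate minor correction and not part of this point.

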5.5.3.3 Dose modification and toxicity management

CyPep-1 dose modifications are not planned. In the event of CyPep-1-related excessive toxicity, administration of CyPep-1 may be delayed for no more than 7 days. Any delay will be per the Investigator's discretion for the management of a patient with excessive toxicity and may consider factors such as recovery from the procedure, scheduling difficulty, or recovery from toxicities. If delayed >7 days, then that dose will be omitted at the discretion of the Investigator with the approval of the Medical Monitor. After 14 days of delay, consult with the Sponsor.

CyPep-1 must be permanently discontinued if a patient experiences:

- A severe systemic hypersensitivity reaction that is uncontrolled with standard management or requires high dose steroids;
- Necrosis, ulcerations, bleeding, or any other serious complication in healthy tissues surrounding the injected tumor; or
- Injected tumor ulcerations that do not show a healing trend in a 3-week period.

In case of pembrolizumab-related toxicity (≥Grade 2 according to the NCI CTCAE v5.0), treatment with CyPep-1 will be delayed until a review is completed by the Investigator and Medical Monitor. If treatment with CyPep-1 is delayed >7 days, then that dose will be omitted. After 14 days of delay, consult with the Sponsor.

Dose modification and toxicity management for immune-related adverse events associated with pembrolizumab

AEs associated with pembrolizumab exposure may represent an immunologic etiology. These irAEs may occur shortly after the first dose or several months after the last dose of pembrolizumab treatment and may affect more than 1 body system simultaneously. Therefore, early recognition and initiation of treatment is critical to reduce complications. Based on existing clinical study data, most irAEs were reversible and could be managed with interruptions of pembrolizumab, administration of corticosteroids, and/or other supportive care. For suspected irAEs, ensure adequate evaluation to confirm etiology or exclude other causes. Additional procedures or tests such as bronchoscopy, endoscopy, and/or skin biopsy may be included as part of the evaluation. Based on the severity of irAEs, pembrolizumab may be withheld or permanently discontinued, and corticosteroids may be administered. Dose modification and toxicity management guidelines for irAEs associated with pembrolizumab are provided in Table 10.

Attribution of toxicity

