8.3 Serious Adverse Event Reporting – Procedures for Investigators

Initial reports

All SAEs occurring from the time of signing the ICF until 90 days (30 days if patients initiate new anti-cancer therapy) after the last dose of study treatment must be reported to Medpace Clinical Safety within 24 hours of the knowledge of the occurrence.

Any SAE brought to the attention of the Investigator at any time outside of the time period specified above must be reported immediately, or within 24 hours of the knowledge of the occurrence, to Medpace Clinical Safety or the Sponsor/designee if the event is considered to be drug-related.

To report the SAE, complete the SAE form electronically in the electronic data capture (EDC) system for the study. When the form is completed, Medpace Safety personnel will be notified electronically by the EDC system and will retrieve the form. If the event meets serious criteria and it is not possible to access the EDC system, send an email to Medpace Safety at [contact] or call the Medpace SAE reporting line (phone number listed below), and fax/email the completed paper SAE form to Medpace (contact information listed in Section 8.6) within 24 hours of awareness. When the EDC system becomes available, the SAE information must be entered within 24 hours of the system becoming available.

Follow-up reports

The Investigator must continue to follow the patient until the SAE has subsided or until the condition becomes chronic in nature, stabilizes (in the case of persistent impairment), or the patient dies.

Within 24 hours of receipt of follow-up information, the Investigator must update the SAE form electronically in the EDC system for the study and submit any supporting documentation (eg, patient discharge summary or autopsy reports) to Medpace Clinical Safety via fax or email. If

it is not possible to access the EDC system, refer to the procedures outlined above for initial reporting of SAEs.

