3.3.9 Study Drug Exposure and Compliance

Duration of Treatment

The duration of treatment (in weeks) for CyPep-1 will be calculated as (the last dose date of CyPep-1 minus the first dose date of CyPep-1 + 14)/7.

The duration of treatment (in weeks) for pembrolizumab will be calculated as the (last dose date of pembrolizumab minus the first dose date of pembrolizumab + 42)/7.

Descriptive statistics will be provided for the treatment duration of CyPep-1 and pembrolizumab for the Safety Analysis Set. Note that the exposure calculation is intended to describe the length of time a patient was exposed to the study drug and therefore does not take study drug interruptions into account.

Total number of cycles initiated

For each patient, the total number of cycles initiated is defined as the total number of cycles that the patient took the study drug recorded on the eCRF(s) during the study. The total number of cycles initiated will be summarized descriptively. In addition, the number and percentage of patients with total number of cycles in the following categories will also be presented: 1 cycle, 2 cycles, 3 cycles, and ≥4 cycles.

Dosing Status

The number and proportion of patients with dose omissions (CyPep-1 and pembrolizumab), dose reductions (CyPep-1 and pembrolizumab), and dose interruptions (pembrolizumab only) will be summarized.

Dosing Intensity

The cumulative dose of (CyPep-1 and pembrolizumab) per patient across the treatment period is the sum of the actual dose (mg) the patient received.

The actual dose intensity will be calculated for each patient as follows:

- Dose intensity of CyPep-1 (mg/week) = cumulative dose of CyPep-1 (mg) /duration of treatment for CyPep-1(in weeks)
- Dose intensity of pembrolizumab (mg/week) = cumulative dose of pembrolizumab (mg) /duration of treatment for pembrolizumab (in weeks)

The overall relative dose intensity (%) for CyPep-1 and pembrolizumab will be calculated as (the actual dose intensity/planned dose intensity per protocol)*100%

All study drug administration data will be listed by patient and tabulated by study arm.

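### SAP 3.7.1 and SAP Appendix E give conflicting treatment-emergence rules, and under 3.7.1 a drug-related SAE starting after day 30 enters no relatedness or fatal-event summary

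*SAP*

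**What the plan says.** SAP 3.7.1 defines TEAEs as "AEs that start or worsen after the first dose of study drug and within 30 days after the last dose of study treatment". Its overview has 17 rows, and 16 of them are restricted to TEAEs or TESAEs. These include the four relatedness rows (CyPep-1-related and any-IMP-related, each for TEAEs and for TESAEs) and the row for TEAEs leading to death. The exception is a general SAE row, which is not split by relationship. Each row also gets a SOC/PT table.

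SAP Appendix E gives another rule. Its first row, for AEs whose start date is known, makes an event treatment-emergent whenever it starts on or after first study drug and sets no latest date. The medication table in the same appendix does carry a limit of 30 days after end of treatment.

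Protocol 8.1 records AEs "from the time of signing the ICF until 30 days after the last dose of study treatment" and SAEs "until 90 days (30 days if patients initiate new anti-cancer therapy) after the last dose of study treatment". Protocol 8.3 adds, for drug-related events, "Any SAE brought to the attention of the Investigator at any time outside of the time period specified above must be reported immediately". SAP 3.7.1 describes collection differently: "AEs will be captured from the date of informed consent through study completion".

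**The concern.** Incidence, frequency and seriousness of TEAEs is a Phase 1b primary endpoint (SAP 2.2.1). SAP 1 says the study ended after Phase 1b, so these tables are the main safety output. Two programmers working from the same SAP could produce different primary-endpoint counts, one from 3.7.1 and the other from Appendix E.

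The choice has a direction. If 3.7.1 is followed, serious events judged drug-related but starting after day 30 leave the summaries that report related serious and fatal events. Leaving them out can only lower those counts. Protocol 8.3 keeps late SAEs reportable precisely when they are considered drug-related, yet relatedness is the split that the tables would lose.

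**Working it through.** The plan states no figure to reproduce. The check sets the rules side by side and counts days.

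**Classification by each rule** (known onset date, days after last dose of study treatment):

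| Event | SAP 3.7.1 | SAP Appendix E | Protocol collection |
|---|---|---|---|
| Serious, day 20 | TEAE | TEAE | yes |
| Serious, day 45, no new therapy | not a TEAE | TEAE | yes (8.1) |
| Serious and drug-related, day 100 | not a TEAE | TEAE | yes, if it reaches the investigator (8.3) |
| Non-serious, day 45 | not a TEAE | TEAE | not required (8.1), although SAP 3.7.1 implies capture |

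The rules agree to day 30 and disagree on every later event.

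**Length of the gap under 3.7.1.** Inputs: SAE collection to day 90 (Protocol 8.1); TEAE window to day 30 (SAP 3.7.1).
- 90 − 30 = 60 days, which is 60/90 = 67% of the post-dose SAE window.
- The SAE window falls to 30 days if new anti-cancer therapy starts. For a patient who starts it within the first 30 days the routine gap is 30 − 30 = 0. Sixty days is therefore a maximum.

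**Can the SAE row recover the lost count?** SAEs are collected from consent, so in event counts SAEs − TESAEs = pre-dose SAEs + late SAEs, with related and unrelated events mixed. Subtraction does not isolate late related SAEs. A reader would have to rebuild that count from the listings.

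**Weight of one event.** Input: six Phase 1b patients (SAP 2.3.5). Suppose one patient has a related SAE on day 45 and there is no other related TESAE:
- Under 3.7.1: 0/6 = 0% (exact 95% CI 0 to 45.9%).
- Under Appendix E, or with a window matched to Protocol 8.1: 1/6 = 16.7% (exact 95% CI 0.4 to 64.1%).

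**The case against.** The strongest reply is that nothing is lost from the report. The general SAE row has no treatment-emergence limit and has its own SOC/PT table. SAEs and AEs leading to death are listed whether or not they are treatment-emergent, and the AE listing shows relationship. With six patients and a descriptive analysis, any late related SAE can be found individually. This is correct and limits the harm, but it does not supply the missing summary or settle which rule applies.

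It can also be said that SAP 3.1.6 presents Appendix E as handling for incomplete dates, so 3.7.1 probably governs. That may be the intent. However, Appendix E has an explicit row for known dates and the SAP states no precedence. Thirty days also matches the protocol's general AE window, and the protocol sets no 90-day TEAE window, so 3.7.1 does not breach a protocol definition. The dose-confirmation rule uses Cycle 1 DLTs and does not depend on these tables.

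Three stronger readings are tempting, and the documents do not support them.
- **Late related SAEs are certain to drop out.** They do so only if 3.7.1 is followed; Appendix E would keep them.
- **The 30-day cut contradicts the exposure formula** in SAP 3.3.9, "last dose date of pembrolizumab minus the first dose date of pembrolizumab + 42)/7". The 42 days are one Q6W interval in an exposure calculation, not a safety window. The 30-day clock also runs from the last dose of the combination. If the last CyPep-1 dose falls d days after the last pembrolizumab dose, the TEAE window ends at day d + 30 after pembrolizumab: day 44 for d = 14 and day 58 for d = 28. A shortfall needs d < 12 and is at most 42 − 30 = 12 days.
- **The 90-day SAE window exists because of late immune-related events.** Protocol 5.5.3.3 does say such events may occur "several months after the last dose of pembrolizumab treatment", but Protocol 8.1 and 8.3 give no reason for the 90 days. The link would be inference.

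**Conclusion.** The SAP contains two incompatible TEAE rules for a primary endpoint, and they should be reconciled before database lock. If 3.7.1 governs, drug-related SAEs starting on days 31 to 90 are collected but absent from all four relatedness rows and from the fatal-TEAE row. The same applies to drug-related SAEs reported after day 90 under Protocol 8.3. The effect runs in the favourable direction. The affected period is at most 60 days per patient, and one affected patient is worth 16.7 percentage points in a table of six.

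This size rests on all six planned patients being in the Safety Analysis Set and on at least one related SAE starting after day 30. The documents do not say whether any did. Because late SAEs remain in the SAE row and the listings, this is a correctable reporting defect. It does not threaten the dose-confirmation decision. The mismatch between capture through study completion and the protocol's 30- and 90-day windows is real but minor.

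**What to change.** State one TEAE rule and use it in both SAP 3.7.1 and Appendix E, including the known-start-date row. Keep 30 days after last dose for non-serious AEs. For serious events, take one of two routes:

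- Define treatment emergence to match Protocol 8.1 (90 days after last dose, or 30 days if new anti-cancer therapy starts) and apply it to TESAEs, related TESAEs and TEAEs leading to death.
- Keep the 30-day definition and add rows for related SAEs and for fatal AEs with onset from first dose onward, regardless of the 30-day cut. This also captures drug-related SAEs reported after day 90 and leaves a single TEAE window.

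In 3.7.1, replace the statement that AEs are captured to study completion with the protocol's collection windows.

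The cost is text edits in two places and a programming flag or a few table rows, using data already collected. The SAE counts may look slightly less favourable, and the first route gives serious and non-serious events different windows, which the table footnotes should state.
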